1.3. Study Rationale

PSMA is an ideal target to develop radiopharmaceuticals for peptide radio-ligand therapy (PRLT) based on small molecule PSMA inhibitors. Studies based on PET and SPECT imaging using ⁶⁸Ga, ¹⁸F, ¹²³I, and ^{99m}Tc labeled small molecule glutamate urea heterodimers have clearly documented the specific localization of these agents in PCa lesions of the prostate gland, and in the distant metastatic lesions.

2. STUDY OBJECTIVES AND ENDPOINTS

2.1. Objectives

2.1.1. Primary Objective

• To evaluate the safety and tolerability of 3 MBq/Kg, but not less than 150 MBq and no more than 250 MBq, of a single i.v. administration of ⁶⁸Ga-PSMA-R2.

2.1.2. Secondary Objectives

- To assess PK, biodistribution, and dosimetry of ⁶⁸Ga-PSMA-R2.
- To establish the optimal imaging method for determining location and burden of positive lesions on ⁶⁸Ga-PSMA-R2 PET imaging in comparison with lesions identified with conventional anatomical imaging scans (CT/MRI and bone scan), and to calculate the agreement of ⁶⁸Ga-PSMA-R2 PET with conventional anatomical imaging on a per patient basis.

2.2. Endpoints

2.2.1. Primary Endpoints

- Incidence and severity of AEs, and SAEs
- Absolute changes and changes from baseline in clinical laboratory parameters (hematology, blood chemistry and urine values), including assessment of shifts from baseline to abnormal values
- Absolute changes and changes from baseline in vital signs & ECG parameters

2.2.2. Secondary Endpoints

- Generation of decay corrected TACs from ⁶⁸Ga-PSMA-R2 PET/CT images in normal organs and tumor lesions.
- Urinary excretion of ⁶⁸Ga-PSMA-R2
- Calculation of half-life of ⁶⁸Ga-PSMA-R2 in blood
- Generation of non-decay-corrected time activity curves from ⁶⁸Ga-PSMA-R2 PET/CT images in normal organs and tumor lesions
- Calculation of residence times in organs and tumor lesions of ⁶⁸Ga-PSMA-R2
- Calculation of absorbed doses and effective whole-body dose of ⁶⁸Ga-PSMA-R2
- To establish optimal threshold, expressed as SUV to discriminate positive PET imaging results from negative ones.
- Burden and location of tumor lesions detected by ⁶⁸Ga-PSMA-R2 in comparison with standard imaging modalities such as CT/MRI and/or bone scan and/or biopsy.
- Calculation of patient level agreement of ⁶⁸Ga-PSMA-R2 PET imaging in prostate cancer patients

3. STUDY DESIGN AND PATIENT POPULATION

3.1. Study Design

This is an open label, multi-center, single dose, Phase 1/2 study to evaluate the safety and tolerability of 3 MBq/Kg, but not less than 150 and no more than 250 MBq, of ⁶⁸Ga-PSMA-R2 in adult patients with PCa expressing PSMA receptors.

This study will consist of 2 phases.

Phase 1:

During the Phase 1 portion of the study, approximately 6 patients with biochemically recurrent PCa will receive the IP and will remain at the site for approximately 6 hours post-injection in order to assess PK, biodistribution, and dosimetry for critical organs. Patients will receive a single dose of 3 MBq/kg, (\geq 150 MBq and \leq 250 MBq), of ⁶⁸Ga-PSMA-R2. The product will be prepared prior to administration and injected intravenously and each patient will undergo a whole-body PET/CT scan following IP administration. Serial blood and urine samples will be collected for PK characterization and dosimetry. Safety assessments will be conducted after IP administration on Day 1, and during follow-up on Days 7 and 28.

Dosimetry will be assessed in 6 patients, they will undergo static whole-body PET/CT images at 0-4 hours to determine absorbed doses by the normal organs and target tumor lesions.

Phase 2:

Two groups of approximately 12 patients will be enrolled in the Phase 2 portion of the study (patients with PCa-BR, and mPCa). Enrollment will be capped at 12 patients in each group to ensure an even distribution of patient condition. If preliminary data analysis from the Phase 1 portion of the study provides sufficient dosimetry data, all patients will undergo whole body PET/CT imaging optimized for time according to the data analysis from the Phase 1 component of the study.

Patients who have signed the informed consent and are eligible for study participation according to the inclusion and exclusion criteria will receive a single intravenous bolus of ⁶⁸Ga-PSMA-R2 on Day 1.

This study is comprised of 4 clinical visits and will be conducted in 3 study periods including: Screening, administration/ imaging, and safety follow-up period (final/early termination).

4. STUDY POPULATION

Up to 30 evaluable patients with histologically confirmed PCa (staged as PCa-BR or mPCa) will be enrolled.

4.1. Inclusion Criteria

- 1. Males, 18 years or older
- 2. Signed and dated written informed consent by the patient prior to any study-specific procedures.
- 3. Histologically confirmed adenocarcinoma of the prostate.
 - a. biochemical recurrence: defined as PSA is ≥ 0.2 ng/mL after radical prostatectomy or PSA nadir plus 2 ng/mL after radiation therapy with corresponding CT/MRI or bone scan revealing absence of local recurrence or metastatic lesions.

OR

- b. metastatic disease: defined as both, castration-sensitive or castration-resistant mPCa (presence of at least one metastatic lymph-node, visceral metastasis and/or bone metastasis).
- c. At least 2 weeks must have elapsed between last anti-cancer treatment administration and the administration of the imaging product, ⁶⁸Ga-PSMA-R2.
- 4. Prior major surgery must be at least 12 weeks prior to study entry.
- 5. Eastern Cooperative Oncology Group (ECOG) performance status 0-2, with a life expectancy ≥ 6 months.
- 6. Adequate bone marrow reserve and organ function as demonstrated by complete blood count, and biochemistry in blood and urine at Screening:
 - Hemoglobin (Hb): >8.0g/dL

- Platelet count of $> 50.000/\text{mm}^3$
- Serum creatinine < 1.5 ´ upper limit normal (ULN) or estimated glomerular filtration rate (eGFR) > 50 mL/min based upon The Chronic Kidney Disease Epidemiology Collaboration (CKD-EPI) equation.
- 8. For male patients with partners of childbearing potential, agreement to use barrier contraceptive method (condom) and to continue its use for 28 days after IP administration.

4.2. Exclusion Criteria

- 1. Pathological finding consistent with small cell, neuroendocrine carcinoma of the prostate or any other histologies different than adenocarcinoma.
- 2. Administered a radioisotope ≤ 10 physical half-lives prior to the day of PET/CT.
- 3. Current severe urinary incontinence, hydronephrosis, severe voiding dysfunction, or need of indwelling/condom catheters.
- 4. Uncontrolled pain or incompatibility that results in patient's lack of compliance with imaging procedures
- 5. Other known co-existing malignancies except non-melanoma skin or low grade superficial bladder cancer unless definitively treated and proven no evidence of recurrence for 5 years.
- 6. Patient with known incompatibility to CT scans.
- 7. Any evidence of severe or uncontrolled systemic or psychiatric diseases, including uncontrolled hypertension and active bleeding diatheses, which in the Investigator's opinion makes it undesirable for the patient to participate in the trial or which would jeopardize compliance with the protocol, or active infection including human immunodeficiency virus (HIV) and untreated hepatitis B, hepatitis C. Screening for chronic conditions is not required.
- 8. Patients who have received any investigational agent within the last 28 days are excluded from participation in this trial.
- 9. Any acute toxicity due to prior chemotherapy and/or radiotherapy that has not resolved according to the Toxicity Grading Scale for Healthy Adult and Adolescent Volunteers Enrolled in Preventive Vaccine Clinical Trials (Section 11.2).
- 10. Known allergy, hypersensitivity, or intolerance to the investigational product or its excipients.
- 11. Patient unlikely to comply with study procedures, restrictions and requirements and judged by the Investigator to be unsuitable for study participation.

4.3. Screen Failures

A "screen failure" is a patient who consented to participate but was not eligible to participate in the study.

For patients not considered eligible after the screening period, the reason for not being eligible must be documented. No additional assessments are needed.

4.4. End-of-Study

End of study will be achieved by a patient after all study procedures and the follow up visit are completed and no further study related activities are required, or when a patient withdraws consent at any time.

Study will be terminated when all patients have completed their end of study activities or at any time due to sponsor decision.

5. STUDY MEDICATION

5.1. Investigational Product for PSMA Imaging: ⁶⁸Ga-PSMA-R2

The full name of the Investigational Product (IP) is "⁶⁸Ga-PSMA-R2 kit for radiopharmaceutical preparation".

The IP is a sterile 2-vial kit which consists of:

- Vial 1: PSMA-R2, 30 µg, powder for solution for injection, to be reconstituted with a solution of gallium-68 chloride (⁶⁸GaCl₃) in HCl eluted from a GMP ⁶⁸Ge/⁶⁸Ga generator;
- Vial 2: Reaction buffer. Vial 2 is to be added to the reconstituted Vial 1.

The kit has to be used in combination with a solution of ⁶⁸Ga in HCl provided by a GMP ⁶⁸Ge/⁶⁸Ga generator to obtain ⁶⁸Ga- PSMA-R2 solution for injection, being the radiolabeled imaging product, which can be directly injected to the patient.

After reconstitution with the eluate from a GMP ⁶⁸Ge/⁶⁸Ga generator and addition of kit reaction buffer (vial 2), the reconstituted solution must be used within 4 hours.

The volume of ⁶⁸Ga- PSMA-R2 solution for injection, corresponding to the radioactive dose to be administered, is calculated according to the estimated time of injection, on the basis of the current activity provided by the generator and of physical decay of the radionuclide (half-life, 68 minutes).

This is a mono-dose product.

Vial 1 is a powder for solution for injection containing PSMA-R2 as active ingredient. The powder is packed in 10 mL Ultra-inert Type I Plus glass vials. Vial 2 Reaction buffer contains no active ingredient. Reaction buffer solution is contained in a 10-mL cyclic olefin polymer vial

The kit will be prepared, packaged and released according to Sponsor Standard Operating Procedures (SOPs), GMP guidelines, International conference on harmonization (ICH) GCP guidelines, and applicable local laws/regulations.

5.2. Investigational Product Packaging, Labeling, and Handling

The investigational product will be supplied by the Sponsor as a sterile, two-vial kit for reconstitution with ⁶⁸Ga solution eluted from approved commercial GMP ⁶⁸Ge/⁶⁸Ga generator.

Labeling will be handled per the Sponsor's SOP. The site personnel will maintain shipping, dispensing, and collection logs provided in Investigator file by the Sponsor or designee (e.g. CRO). The IP will be inventoried according to the protocol instructions and applicable regulations and will be stored in a secure, locked place with limited authorized access at the investigational site.

After reconstitution with ⁶⁸Ga solution eluted from approved commercial GMP ⁶⁸Ge/⁶⁸Ga generator, the investigational product is a radioactive substance, and it must be handled and administered by qualified/authorized personnel only, and must be prepared in accordance with pharmaceutical quality requirements and radiation safety regulations.

5.3. Investigational Product Administration and Accountability

When investigational product is received at the site, the Investigator, Pharmacist or authorized designee shall check for accurate delivery and acknowledge receipt by signing and dating the shipping documentation, and returning the reception form to the Sponsor or designee. A copy of this documentation shall be retained for the Investigator file.

Any use or manipulation of the IP shall be carefully recorded on the IP accountability form provided by the Sponsor, and an accurate accounting must be available for verification by the clinical research associate (CRA) at each monitoring visit.

IP accountability records shall include:

- confirmation of the IP delivery to the study site;
- inventory at the study site;
- use of IP by each patient; and
- it should include delivery dates, quantities, lot/batch numbers and manufacture/expiration dates for the IP. Investigators should maintain records to document adequately that:
 - the patients were administered the doses specified by the protocol and any amendment(s);
 and
 - all IP provided by the Sponsor were fully reconciled.

Unused investigational product must be destroyed per local practice.

The administration volume (containing the planned dose) is determined according to the estimated time of injection, on the basis of the physical decay of the radionuclide (half-life, 68 minutes).

5.4. Patient Release and Radioprotection Precautions

Following administration of ⁶⁸Ga-PSMA-R2, patients should remain at the clinical site for an additional 6 hours in an area with suitable radiation shielding to protect others from unnecessary exposure. At the time of release, patients are given written instructions which outline the precautions the patient must take to minimize radiation exposure to people around them.

Excessive release of hormones or bioactive substances are not expected to occur following treatment, therefore, observation of patients by overnight hospitalization is not required.

5.5. Concomitant Medications

Previous and concomitant medications will be coded using World Health Organization (WHO) dictionary. Type and incidence of previous and concomitant medications will be tabulated (generic terms).

All medications taken at the start of Screening until the end of the study, or early termination, are to be recorded. This includes prescription and over-the-counter medications taken during this time frame.

5.6. Prohibited Concomitant Medications and Procedures

While participating in this study cancer targeted therapy including but not limited to chemotherapy, hormonal therapy (except for LHRH or GnRH), or external beam radiation is not permitted within four weeks prior to ⁶⁸Ga-PSMA-R2 PET/CT scan.

Any medications which are considered necessary for the patient's welfare, may be given at the discretion of the Investigator; however, if it belongs to the list above the patient will have to be withdrawn from the study treatment.

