	 During the first part (Phase 1), approximately 6 patients with biochemically recurrent PCa will receive the investigational product (IP) and will remain at the site for approximately 6 hours post-injection in order to assess the PK, biodistribution vs. time, and dosimetry for critical organs. Patients will receive a single dose of 3 MBq/kg, (≥ 150 and ≤ 250 MBq), of ⁶⁸Ga-PSMA-R2 intravenously. Serial blood and urine samples will be collected for PK characterization and dosimetry and whole-body PET/CT will be acquired at selected time points (0-4 hours) to determine organ and tumor absorbed doses. Safety assessments will be conducted after IP administration on Day 1, and during follow-up on Days 7 and 28.
	• In the second part of the study (Phase 2), two groups of approximately 12 patients will be enrolled (patients with PCa in biochemical recurrence (PCa-BR), and patients with prostate cancer in the metastatic stage (mPCa)). Enrollment will be capped at 12 patients in each group to ensure an even distribution of patient conditions. If preliminary data analysis from the Phase 1 part of the study provides sufficient dosimetry data, all patients will undergo whole body PET/CT imaging optimized for time (up to 2 time points) according to the data analysis from the Phase 1 component of the study.
Study Population	Patients with histologically confirmed adenocarcinoma of prostate staged as PCa-BR or mPCa
Study Duration	Approximately 6 weeks: up to 2 weeks of screening assessment, a 1-Day IP administration and imaging period, and three safety follow-up visits, at least one hour after the administration, then 7 Days and 28 Days after the administration. End of the study is defined as the date the last patient enrolled completes the 28 Days safety follow-up.
Treatment Duration	One Day/single IP administration
Number of Patients	Approximately 30 patients will be enrolled in this trial.
Planned	Phase 1 will include approximately 6 patients with adenocarcinoma of prostate origin staged as PCa-BR.
	Phase 2 will be comprised of 2 groups: one of approximately 12 patients with PCa- BR and another of approximately 12 patients with mPCa.
Inclusion Criteria	1. Male patients, 18 years of age or older.
	2. Signed and dated written informed consent by the patient prior to any study- specific procedures
	3. Histologically confirmed adenocarcinoma of the prostate.

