6.2. Screening Visit (Day -14 to Day -1)

Each patient will be allocated a unique patient ID number, which will identify the patient throughout the study.

During the Screening visit, the following activities will be performed:

- Written informed consent will be obtained prior to performing any study related activities
- Inclusion/exclusion criteria will be checked.
- Each patient's demography: date of birth, gender, ethnicity, weight, height, medical history, and relevant baseline characteristics will be recorded.
- Historic and current prostate cancer related biopsies (prostate and metastatic sites) should be performed per local practice. All data related to date of biopsy, site of lesion, and pathology results will be collected in the database.
- ECOG performance status must be assessed (Section 11.1). The medical history will be recorded as well as all concomitant medications taken including therapies for PCa.
- All patients will have undergone histological/immunohistochemical exam at the time of the original PCa diagnosis and CT/MRI exam, within two months before enrollment.
- Vital signs will be assessed.
- ECG (12-lead) will be recorded.
- Blood samples for PSA, hematology, blood chemistry and urinalysis will be obtained.
- All concomitant medications including PCa therapies taken 2 weeks prior to the IP administration date through the end of study will be recorded.
- Any AEs occurring after the ICF signature will be recorded and followed until resolution.

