6.3. Administration/ Imaging Period (Day 1)

Eligible patients who have met all inclusion criteria and none of the exclusion criteria will receive an injection of 3 MBq/Kg, but not less than 150 MBq and no more than 250 MBq of ⁶⁸Ga-PSMA-R2. Patient will enter the trial unit on the morning of the exam. Each subject will be allocated one single imaging kit.

- All concomitant medications including PCa therapies taken 2 weeks prior to the IP administration date through the end of study will be recorded.
- Any AEs occurring after the ICF signature will be recorded and followed until resolution.
- Vital signs will be assessed before and after the ⁶⁸Ga-PSMA-R2 injection and at the end of the PET/CT exam.
- ECOG performance status will be assessed.
- Patient will be injected intravenously one single bolus dose of ⁶⁸Ga-PSMA-R2.
- ECG (12-lead) will be recorded immediately after IP administration.

- For patients entering in Phase 1: PET/CT scans will be performed at approximately 20-30 minutes and at 1, 2, 3-4 hours post-injection.
- Patients in the Phase 1 portion of the study will undergo distribution/ dosimetry analysis
- For patients entering Phase 2, patients will have PET/CT imaging reduced to up to 2 whole body scans within the optimal time frame, to confirm the high tumor to background ratio, and agreement compared to standard conventional method.
- Samples for hematology, biochemistry and urinalysis will be collected after the administration of IP.
- Patients entering Phase 1 only: PK and dosimetry blood samples will be collected immediately prior to IP administration, approximately 5, 10, 20, 40 minutes, as well as immediately after, 1, 2, 4, and 6 hours post IP administration.
- Patients entering Phase 1 only: Urine sample for PK will be collected Pre-injection, approximately 0-20 minutes after IP administration, 0-1 hour, 1-2 hours, 2-4 hours, 4-6 hours post-injection.

6.4. Safety Follow-up Visits (Day 7 ± 2 Days and Day 28 ± 3 Days)

After IP administration, two safety follow-up visits will be performed on Day 7 (\pm 2 Days) and Day 28 (\pm 3 Days).

- All concomitant medications including PCa therapies taken 2 weeks prior to IP administration date through the end of study will be recorded.
- Any AEs occurring after the ICF signature will be recorded and followed until resolution.
- ECOG performance status is assessed.
- Vital signs will be assessed.
- Blood samples for hematology, biochemistry and urinalysis will be obtained.

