12.2. PRIOR AND CONCOMITANT NON-CANCER MEDICATIONS

Medications will be presented for the FAS and PPS and coded using WHO Drug Dictionary version MAR2018 or higher if available at the time of the Database Lock. The medications will be summarized by WHO-DD Preferred Names, sorted by decreasing frequency based on total count.

Document:	K:\AAA\Ga-PSMA-R2\VYA27826\ Biostatistics\Documentation\SAP\v2.0\Ga-PSMA-R2-SAP_v2.0
Author:	 Version Number: 2.0

Template No.: CS_TP_BS016 Revision 5
 Effective Date: 01Apr2018

Version Date: 29JUN2020

Reference: CS_WI_BS005

See APPENDIX 2 for handling of partial dates for medications, in the case where it is not possible to define a medication as prior or concomitant, the medication will be classified by the worst case; i.e. concomitant.

- Prior medications are those which started prior to the day of first and single dose of study medication.
- Concomitant medications are those which:
 - started prior to, on or after the first and single dose of study medication,
AND
 - ended on or after the date of first and single dose of study medication or were ongoing at the end of the study.

All prior and concomitant prohibited/restricted medications outlined in protocol section 5.6, as determined by the medical advisor, will be listed.

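### Inclusion 3c and section 5.6 of the protocol set different anti-cancer washouts with different exceptions, so the same patient can be eligible and in breach

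*Protocol*

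**What the plan says.** **Eligibility.** Protocol section 4.1, criterion 3c, and the same criterion in the synopsis: "At least 2 weeks must have elapsed between last anti-cancer treatment administration and the administration of the imaging product". It names no class of treatment and makes no exception.

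**Prohibited therapy.** Protocol section 5.6 covers "cancer targeted therapy including but not limited to chemotherapy, hormonal therapy (except for LHRH or GnRH), or external beam radiation", which "is not permitted within four weeks prior to" the PET/CT scan. It then allows medication needed for the patient's welfare at the investigator's discretion, but "if it belongs to the list above the patient will have to be withdrawn from the study treatment".

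**Who is dosed.** Protocol section 6.3: "Eligible patients who have met all inclusion criteria and none of the exclusion criteria will receive an injection". The text does not refer to section 5.6 at that point.

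**Timing.** The synopsis describes "a 1-Day IP administration and imaging period".

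**Recording.** Protocol section 6.2, repeated in substance in sections 6.3 and 6.4: "All concomitant medications including PCa therapies taken 2 weeks prior to the IP administration date through the end of study will be recorded".

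**Analysis.** SAP section 12.2: "All prior and concomitant prohibited/restricted medications outlined in protocol section 5.6, as determined by the medical advisor, will be listed". The SAP gives no washout length of its own. SAP section 5.3 removes patients with critical or major deviations from the Per Protocol Set.

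**The concern.** Two operative passages govern the same interval and give different answers, and nothing else in the protocol settles which prevails. A site that applies the eligibility list correctly can dose a patient whom section 5.6 prohibits. A site that applies section 5.6 as a further entry condition will turn that patient away. The same history can thus produce an evaluable patient with no deviation, an evaluable patient with a prohibited-therapy deviation, or a screen failure.

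What is at stake is consistency across about four sites: who may be scanned, what is logged as a deviation, and possibly who belongs to the Per Protocol Set. The SAP's listing of prohibited medications takes its definition from section 5.6, so it can flag patients whom the eligibility criteria admitted.

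**Working it through.** The protocol states no figure to reproduce. The check sets the two rules against each other.

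**Inputs**
- Criterion 3c (section 4.1 and synopsis): 2 weeks = 14 days, counted to administration.
- Section 5.6: four weeks = 28 days, counted to the PET/CT scan.
- Administration and scan share a one-day period (synopsis), so both count back from Day 1.
- Screening runs from Day -14 to Day -1 (section 6.2). Under SAP section 6.2, Day -14 is 14 days before Day 1.

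**Rules.** Let d be the number of days from the last treatment to Day 1. Criterion 3c is met if d ≥ 14. Section 5.6 is breached for a listed therapy if d < 28, or d ≤ 28 if day 28 counts as falling within four weeks.

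| d (days) | 3c | 5.6, listed therapy | 5.6, LHRH/GnRH |
|---|---|---|---|
| 0 to 13 | not met | breached | exempt |
| 14 to 27 | met | breached | exempt |
| 28 | met | depends on reading | exempt |
| 29 or more | met | not breached | exempt |

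**Result 1: listed therapies.** The rules conflict for d = 14 to 27, a band of 28 − 14 = 14 days. Counting day 28, it is 15 days. Example: chemotherapy 21 days before Day 1 satisfies 3c (21 ≥ 14) and breaches 5.6 (21 < 28).

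**Result 2: LHRH/GnRH.** The conflict runs the other way for d = 0 to 13. These agents are exempt under 5.6 but fail 3c if they count as anti-cancer treatment, which 3c does not say. The question is a practical one, since castration-sensitive and castration-resistant metastatic patients are both eligible and SAP section 11.2 tabulates pharmacological castration.

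**Does another criterion resolve it?** No. The only 28-day exclusion on prior agents (exclusion 8 in section 4.2) concerns investigational agents.

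**Recording.** A 2-week look-back reaches d = 14. Of the 14 days in the conflict band, d = 15 to 27 (27 − 15 + 1 = 13 days) lie outside that wording.

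**The case against.** **Section 5.6 governs conduct, not entry.** It opens by referring to participation in the study, so it could be read as applying only after consent. This does not rescue the text. Participation before the scan lasts at most the 14 days of screening, and 3c already rules out d below 14. On that reading the four-week figure could bite only at d = 14, so it would have almost no effect and would still need correcting.

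Four stronger readings are tempting, and the documents do not support them.

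- **Every patient in the band must be withdrawn.** The withdrawal sentence most directly addresses medication given at the investigator's discretion. Therapy at 15 to 27 days predates the screening window, and the text does not clearly extend withdrawal to it. What stands is that its reach is unclear.
- **Breaches will go unrecorded.** SAP sections 12.1 and 12.4 report prior cancer therapies and prior radiotherapy with no look-back limit, the former from a dedicated eCRF page. Protocol section 6.2 also asks for prostate cancer therapies alongside the medical history. What stands is a mismatch in the recording wording, not a shown data gap.
- **The imaging analyses pool patients under no rule at all.** If dosing follows section 6.3, every dosed patient shares the 2-week minimum of 3c. What can differ is whether a site also turned away patients in the 14-to-27-day band.
- **The Per Protocol Set shifts by a calculable amount.** One patient is 1/12 = 8.3% of a Phase 2 group, 1/18 = 5.6% of the planned PCa-BR patients (6 + 12) and 1/30 = 3.3% overall. These are only the weight of one patient. The documents do not say how many fall in the band, a 5.6 breach need not be graded critical or major, and SAP section 4.3 makes repeating the final analysis on that set optional.

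**Conclusion.** The contradiction holds. For therapies listed in section 5.6, a patient treated 14 to 27 days before Day 1 is both eligible and prohibited. For LHRH/GnRH, the opposite conflict covers days 0 to 13, provided these agents count as anti-cancer treatment under 3c. Both results assume that injection and scan take place on the same day, as the synopsis says.

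The consequence is that eligibility and prohibited-therapy deviation status depend on the passage a site follows. Per Protocol membership does so only if the breach is graded critical or major, a decision that SAP section 5.3 leaves until before database lock. Primary safety outputs use the Full Analysis Set, defined by dosing, and that definition is unaffected. No effect on any estimate can be sized from the documents. The point should be corrected because the same patient can be handled in opposite ways, not because a result is shown to be biased.

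**What to change.** 1. Reconcile criterion 3c, in both the synopsis and section 4.1, with section 5.6 as one rule. State the same therapy classes and exceptions in each place, including how LHRH/GnRH is treated and whether the boundary day counts. The interval is a clinical choice for the sponsor and none is proposed here.
2. State whether the withdrawal sentence in section 5.6 applies to therapy given before consent or only to therapy started during participation.
3. Align the 2-week recording wording in sections 6.2 to 6.4 with the rule that is kept. First check whether the data behind SAP sections 12.1 and 12.4 already hold the therapies and dates needed. If they do, a cross-reference is enough.

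The cost is protocol wording in a few places and, if the check in step 3 shows a need, one data-entry instruction. No procedure, visit or patient is added. The SAP refers to section 5.6 without stating an interval, so its prohibited-medication listing would follow the reconciled text.
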